When in the direct contact with even a small amount of blood, the compound forms an occlusive seal through simultaneous iron-mediated agglomeration of blood solids/proteins and rapid dehydration of the blood. Seal formation is independent of the clotting cascade, facilitating sealing regardless of anticoagulation / antiplatelet status of the patient. Following cessation of pressure being applied to the site, the remnants of StatSeal form what resemble a 'scab', and remains in place for 24 hours, covered with a band-aid or Tegaderm patch.

In clinical testing using a protocol refined at the University of Miami Miller School of Medicine, the use of this compound in conjunction with commercially available hemostasis bands has demonstrated the potential to significantly shorten the time required to achieve hemostasis^{11,12}. Further, these results demonstrated the ability to achieve hemostasis using StatSeal with similar, or fewer complications when compared to standard methods, and did so regardless of the patient's anticoagulation status.

INDICATION FOR USE

StatSeal Advanced is a commercially available product in the United States, and is indicated for use on patients in whom the radial artery has been used to gain vascular access for a cardiovascular procedure.

DEVICE STORAGE AND ACCOUNTABILITY

StatSeal Advanced is provided in a sterile, foil pouch to protect it from humidity / moisture. As with most medical products, it should be stored in a cool, dry, secure environment. StatSeal Advance will be provided at no charge by the manufacturer for use in the study.

Damaged devices will be returned to the manufacturer (Biolife, LLC, Sarasota,FL). All unused devices may be retained by the site for continued use, if they so choose.

III. STUDY OBJECTIVE(S)

The primary objectives of this study are to evaluate the performance of StatSeal Advanced used in conjunction with the TR Band (SSA) as compared to the TR Band without SSA (TRB) relative to:

1. the incidence of peri-procedural radial artery occlusion (RAO) at discharge or 24 hours, whichever occurs first, and;
2. the Time to Hemostasis (TTH)

HMS is defined as the Hemostasis Management System employed based on which group the patient is randomized to (either SSA or TRB).

Radial Artery Occlusion is defined as the absence of flow to the hand based upon plethysmography – pulse oximetry (Pleth-Ox) performed using the Barbeau scale.

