Time to Hemostasis (TTH) is defined as the time period required to achieve hemostasis, more specifically the time during which the subject is wearing the HMS system and the system is active, e.g. applying compressive force to the access site. For clarity, the time period that a HMS is left on the wrist while totally deflated is not considered as part of the TTH time.

IV. STUDY DESIGN AND METHODOLOGY

STUDY DESIGN

This study is a physician initiated, prospective, observational, two arm, randomized study to be performed at up to four experienced 'Radial First' centers. A minimum of 120 patients having undergone successful radial catheterization will be enrolled in the study, 60 in each arm.

Enrollment will continue at each site on discretion of the investigators until each center enrolls a minimum of 30 patients, or a maximum of 180 patients are enrolled. Clinicians will perform the catheterization in accordance with local standard practice, with a minimum of 5,000 units of unfractionated heparin for anticoagulation.

STUDY METHODS:

Patient Selection Criteria Study subjects will be identified in the catheterization laboratory holding area and asked to sign the informed consent prior to their catheterization procedure before the administration of sedative agents.

Inclusion Criteria:

- Patient undergoing diagnostic angiography or PCI via the radial artery
- Patients with a Barbeau test prior to the procedure showing pattern A,B,or C.

Exclusion Criteria:

Candidates for this study will be excluded if any **one** of the following criteria is true.

- Use of a radial sheath larger than 6 Fr (a 7Fr-in-6 Glidesheath Slender[®] is allowed).
- Use of an anticoagulant other than unfractionated heparin or bivalirudin.

- Any anticipated need for continued anticoagulation post-catheterization. Glycoprotein inhibitors are acceptable.
- Any active treatment with oral anticoagulants continued during course of procedure.
- Presence of arteriovenous dialysis fistula in the ipsilateral arm.
- Any physical deformity or trauma / injury of either wrist that would prevent proper placement or function of the hemostasis band.
- Raynaud's syndrome or known peripheral vascular disease of the forearm.
- Mental incompetence or inability to follow the instructions to complete the study.
- History or presence of Radial Artery Occlusion.
- Barbeau test showing Pattern D.
- Patients undergoing catheterization from the femoral or ulnar artery approach.

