Diabetes: Hgb A1C >6.5% or active medical treatment for diabetes.

Hypercholesterolemia: LDL >130 or on treatment with antilipemic agents.

Hypertension: >140/80 or on medical treatment for hypertension.

Diagnostic procedure: Involving diagnostic catheters only.

Interventional procedure: Involving an interventional wire and therapeutic ACT typically >200, including for fractional flow reserve measurement where a stent is not placed.

Single wall puncture: Use of micropuncture wire and anterior wall puncture only.

Double wall puncture: Use of double wall puncture and sheath withdrawal technique.

Number of forward attempts: Number of forward advancements of the needle required to obtain access (not number of separate punctures of skin).

Procedure Start Time: Time when lidocaine is administered, prior to first puncture attempt.

Procedure End Time: Time when sheath is removed.

Test methodology:

All Pleth-ox testing will be done by qualified personnel with results classified according to Barbeau test pattern classifications. [Barbeau, et al. *Evaluation of ulnopalmar arterial arches with pulse oximetry and plethysmography; comparison with the Allen's test in 1010 patients. Am Heart Journal; 2004; 147:489-493*]

At the start of the TRA procedure, prior to radial artery cannulation, a baseline Pleth-ox exam will be performed for all patients and recorded on the CRF. Ulnar compression will be applied to confirm that the radial artery is patent. Patients with a type D pattern exam will be excluded from the study.

At the conclusion of a successful transradial procedure, the patient will be randomized to either SSA or TRB, each device applied per protocol & IFU.

Following placement of the HMS system, Pleth-Ox exams will be performed at the following time points with results recorded in the CRFs.

- Within 5 minutes of initial HMS placement
- In the SSA (StatSeal Advanced) group, within 5 minutes of the first partial deflation (20 minutes after initial placement).
- Within 5 minutes of full deflation of the HMS in both groups
- Within 30' of discharge or 24 hours post procedure (\pm 1 hour), whichever occurs first.

VI. STUDY STATISTICAL PLAN:

This is a physician initiated, prospective, randomized, two-arm study, to be conducted at up to four experienced 'Radial First' centers with the principal investigator having a (minimum) ten case experience using StatSeal Advanced.

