The sample size of 120 patients is estimated to have 90% power to detect an average difference in time to removal of the TR band of 60 minutes between the SSA and TRB groups, using a relatively large standard deviation of 100 minutes and a two-sided alpha of 0.05.

Descriptive summary statistics will be presented for all study variables. Continuous variables will be displayed as means with standard deviations and medians with 75th and 25th percentiles. Categorical variables will be summarized as frequencies with their respective percentages with two-sided 95% exact confidence intervals of the percentages. Statistical comparisons for continuous variables will be performed using the Student's t test or Mann-Whitney U test, as appropriate. Comparisons for categorical variables will be performed using the Chi square test or Fisher exact test, as appropriate. A two-sided P value of 0.05 will be considered statistically significant.

Categorical variables will include, but are not limited to:

- Percent of patients in each arm with total TTH of 60 minutes or less.
- Percent of patients in each arm with TTH of 40 minutes or less without complication.
- The percentage of patients in each arm with bleeding, oozing or hematoma during TTH, further delineated by the EASY bleeding and hematoma classification attached.
- Percent of patients in each arm with RAO at each /all follow-up points.
- Percent of patients in each arm with radial patency as tested with Pleth-ox at each designated test time point.

Primary Efficacy Outcomes:

In each arm the:

- Total Time to Hemostasis (TTH), defined as the total time the HMS applies compressive force until successful hemostasis is achieved without complication.

Secondary Efficacy Outcomes:

In each arm the:

- Percent of patients free from radial artery occlusion at discharge or at 24 hours, whichever occurs first.
- Percent of patients with Barbeau test patterns A,B,C,D at initial application of the HMS
- Percent of SSA patients with Barbeau test patterns A,B,C,D after 20' of HMS time.
- Percent of patients with Barbeau test patterns A,B,C,D at full deflation of the HMS. (40' for SSA group; per protocol in the TRB group)
- Percent of patients with Barbeau test patterns A,B,C,D at discharge or at 24 hours, whichever occurs first.
- Percent of patients in whom successful hemostasis is achieved in one hour or less.

Primary Safety Outcome:

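### Does the written definition of radial artery occlusion (RAO) fail to match the exam that measures it?

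*Protocol*

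**What the plan says.** RAO is the first of the two primary objectives in Section III of the protocol and a secondary efficacy outcome in Section VI: "Percent of patients free from radial artery occlusion at discharge or at 24 hours, whichever occurs first". The definition, also in Section III, reads "Radial Artery Occlusion is defined as the absence of flow to the hand based upon plethysmography" and goes on to name pulse oximetry, "performed using the Barbeau scale".

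Under Test methodology in Section V, all such exams are graded by Barbeau pattern. For the baseline exam it adds: "Ulnar compression will be applied to confirm that the radial artery is patent". A type D pattern at that exam excludes the patient. The manoeuvre is not restated for the exams after band placement.

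Two exclusion criteria in Section IV stand side by side: "History or presence of Radial Artery Occlusion" and "Barbeau test showing Pattern D". The list of categorical variables in Section VI has two related lines: "Percent of patients in each arm with RAO at each /all follow-up points" and "Percent of patients in each arm with radial patency as tested with Pleth-ox at each designated test time point". The three safety outcomes in Section VI set RAO aside and refer to the protocol's definition of it. The SAP does not define RAO.

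**The concern.** Flow to the hand and flow through the radial artery are different things. With a blocked radial artery and a healthy ulnar artery the hand is still perfused. A site that took the definition at its word, and did not compress the ulnar artery at discharge, could record no occlusion where there is one. RAO would then be under-counted for an outcome the protocol treats as important.

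Two smaller points add to the impression of looseness.

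- The RAO line in Section VI does not list its follow-up points. Some exams are made while the band is inflated, and loss of signal there may be intended compression and not occlusion.
- The control-arm text in Section IV times exams by band removal and by a point after 24 hours. Section V speaks of full deflation and of the earlier of discharge and 24 hours, with one hour either way.

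**Working it through.** **1. What the sample size rests on.** Section VI uses a 60-minute difference in time to band removal, SD 100 minutes, two-sided alpha 0.05 and 90% power. Per arm, n = 2 × (1.960 + 1.282)² × (100/60)² = 2 × 10.51 × 2.778 = 58.4, rounded up to 59. The t-test version gives 59.35, rounded up to 60 per arm, or 120 in total. The stated figure reproduces, and RAO is not an input.

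**2. Definition against exam.** The definition has three parts: absent flow to the hand, plethysmography with oximetry, and the Barbeau scale. The only manoeuvre described for a study exam is ulnar compression, at baseline. The background section uses the same logic when it describes occluding the ulnar artery to show antegrade radial flow. With the ulnar artery compressed, any signal in the hand comes through the radial artery, so the two readings of flow coincide. They part only if the ulnar artery is left open, which the protocol nowhere describes for a study exam. Pattern D is the pattern that disqualifies a patient at the exam meant to confirm radial patency, so it is the natural no-flow category.

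**3. The two exclusions.** A history of occlusion reaches past events that a same-day pattern D cannot show. Listing both does not imply that they mean different things on the day.

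**4. Exams with air in the band.** From Section V:

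| Arm | Exams | With air in band |
|---|---|---|
| TR Band alone | placement, full deflation, discharge/24 h | 1 of 3 |
| StatSeal plus TR Band | placement, partial deflation, full deflation, discharge/24 h | 2 of 4 (8 cc, then 8 − 3 = 5 cc) |

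Pooling all exams would mix compression with occlusion, and unevenly: Section IV calls 8 cc typically occlusive, whereas the control band is let down until bleeding occurs and then given 2 ml back. But the line allows reporting at each point, Section VI has its own patency line for every test time, and patterns A to D are tabulated exam by exam. Under-band readings therefore stay separable. The discharge/24-hour outcome does not use them.

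**5. Exam times.** Section V's final exam window is 24 ± 1, or 23 to 25 hours. The control text says after 24 hours. An exam at 24 to 25 hours meets both. Sections III, V and VI all say that the earlier of discharge and 24 hours applies. The control text also defers to the exam method set out further on, which is Section V's single schedule for both groups. Full deflation and removal are 60 − 40 = 20 minutes apart in the StatSeal arm; no such gap is given for controls.

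**6. What a literal reading could do.** Expected cases per arm are 60 × r, with r the 5-10% background rate: 60 × 0.05 = 3.0 and 60 × 0.10 = 6.0. Suppose a share m of occlusions is missed. Expected cases are 60 × r × (1 − m), and the chance of none is (1 − r(1 − m))^60.

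| m (assumed) | Cases, r = 5% | P(none) | Cases, r = 10% | P(none) |
|---|---|---|---|---|
| 0 | 3.0 | 4.6% | 6.0 | 0.2% |
| 25% | 2.25 | 10.1% | 4.5 | 0.9% |
| 50% | 1.5 | 21.9% | 3.0 | 4.6% |
| 75% | 0.75 | 47.0% | 1.5 | 21.9% |

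The documents give no basis for any m above zero, so the table shows sensitivity only. If m is the same in both arms, (1 − m) cancels from the risk ratio.

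**7. What the RAO comparison can show anyway.** With every case correctly found, Fisher's exact test at 60 per arm has about 9% power for 10% against 5%, and about 2% for 5% against 2.5%.

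**The case for a change.** The best case for a change is that analysts cannot repair a manoeuvre that was not done. If a site leaves the ulnar artery open at discharge, a recorded pattern A, B or C may hide an occlusion, and tabulating the patterns will not reveal it. Counts are small enough for one patient to matter: with 60 per arm, 5 against 0 gives p = 0.057 and 6 against 0 gives p = 0.027. The remedy would be a few words.

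Part of this stands. The visible text names no pattern as RAO and states ulnar compression only at baseline. What does not stand is the step from there to a wrong result. The mismatch at the discharge exam is an inference, since the text is silent there and does not prescribe a different method. The exams are graded by qualified staff at experienced radial centres, who have just done the baseline test on the same patient. The sensitivity to one patient comes from few events and would remain under any wording. It is also a stretch to count the three safety outcomes as resting on the definition: they exclude RAO, and one concerns complications away from the access site.

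**Conclusion.** The concern does not hold as a reason to change the plan. The definition could be fuller, but its natural reading, pattern D during ulnar compression, is workable, agrees with the only exam described, and is what radial operators and an analyst would apply. The discharge/24-hour outcome is fixed in time, under-band readings can be kept apart with the tabulations already planned, and the control-arm exam times are a slip of wording that Section V's common schedule settles.

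In size, 3 to 6 RAO cases are expected per 60 patients at the 5-10% rate. The background section gives less than about 5% with patent hemostasis, which would mean fewer than 3. No misreading is shown, no bias in the risk ratio follows if any misreading is equal in the arms, and the sample size is unaffected.

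This rests on two assumptions: that sites repeat the baseline manoeuvre at the full-deflation and discharge/24-hour exams, and that analysts do not pool under-band readings into RAO. The case report forms and the study graphic, which may state the rule, were not in the reviewed copy. RAO's differing rank in Sections III and VI is a separate matter.

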- Cardiogenic shock or any clinical instability as assessed by the physician performing the procedure.

Transradial Catheterization Procedure

Transradial Cardiac Catheterization will be performed according to local practice standards with use of a sheath diameter of up to 6 Fr. (A 7Fr-in-6 Glidesheath Slender®, with an outer diameter of 6Fr is defined as a 6F sheath and is allowed.) In accordance with current recommendations for minimizing radial artery occlusion, a minimum of 5,000 units of unfractionated heparin, or therapeutic bolus of bivalirudin, will be administered to all patients enrolled in the study.

Patients will have their activated clotting time measured at least 5 minutes following the initial dose of anticoagulant, although every patient receiving 5,000 units of heparin will be eligible for the study. Vasodilators (nitroglycerin, verapamil) will be administered in accordance with local practice.

Timing of Subject Enrollment

A subject will be consented into the study prior to the administration of sedation prior to the procedure, and randomized at the conclusion of a successful procedure (after all anticoagulation and antiplatelet medication decisions have been made), at which time placement of the assigned HMS device will occur. Eligibility for the study will be assessed at this time and the subject will have to meet all of the inclusion criteria and none of the exclusion criteria.

Randomization will be performed by means of sealed envelopes in randomization blocks of 30. Each envelope will be labeled by patient number containing device designation. Device designation in the envelopes will be random in occurrence. When a patient is officially enrolled (after successful completion of a TRA procedure), the envelope corresponding to that patient number in the Study Patient log will be pulled, opened, and the assignment revealed.

Each of 4 sites will be allotted an initial block of 30 envelopes, and sets of backup blocks of 30 envelopes. On the discretion of the site principal investigator and the lead principal investigator, enrollment may continue until each site enrolls 30 patients. The maximum enrollment at any one site shall not exceed 50% of the total study enrollment, or 90 patients.

End of Study Status / Effect of Withdrawals:

A subject will have completed the study when one of the following events is documented:

1. The patient is successfully enrolled, treated with a HMS, and completes all required follow up tests.

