Each subject in the study must sign the informed consent agreeing to participation.

Alternatives to Participation

As a voluntary randomized study, the patient's alternative to participation is primarily to the local standard of care, typically involving the TR band, used per local protocol (typically 1-3 hours of application). SSA devices may be used outside of the study depending on local practice and availability.

Study Activities

The Investigator is required to perform the study in accordance with the protocol and to use the HMS per the instructions for use.

Follow-Up

There is no requirement for the subjects taking part in the study to be seen or examined for any follow up relative to the study following completion of activities described herein.

CRFs

CRFs will be completed for each subject. See Appendix 1 for the CRFs.

Records and Retention

Copies of all records will be retained by the investigator at each site for 2 years.

(Model) Patient Informed Consent

See Appendix 2 for a model of the informed consent.

Communication with the Principal Investigator:

All communication regarding the study should be routed directly to the Principal Investigator.

Copies of all correspondence regarding the study should be maintained in the Site Investigator study file.

Declaration of Helsinki & HIPPA

The Principal Investigator will ensure that this study is performed in conformity with the Declaration of Helsinki, HIPPA, and all local and national regulations.

Investigator Responsibilities

- Sign and adhere to the Investigator Agreement
- Sign and adhere to all of the required elements of the Clinical Protocol
- Resolve queries in a timely manner
- Participate in Investigator meetings, if scheduled
- Comply with the Declaration of Helsinki
- Obtain written Informed Consent from each study participant before any study specific procedures are performed
- Complete all required case report forms (CRFs) for each subject
- Comply with all applicable regulations and codes of approvals from the site IRB and other Regulatory Authorities
- Notify the Principal Investigator of personnel changes that may affect the study protocol
- Retain all records and study files as required, after which the files may be destroyed.
- Allow direct access to source data/documents, including patient records, in case of monitoring, auditing and/or inspection by the IRB and/or other regulatory authority bodies.

X. RISK BENEFIT ANALYSIS

General Risks and Presumed Benefits:

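### One fixed block length of 30, printed in the site protocol and matching the site enrolment figure, makes the end of each completed block deducible just before an unmasked eligibility decision

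*Protocol*

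**What the plan says.** Protocol section IV, Timing of Subject Enrollment, sets out the mechanism: "Randomization will be performed by means of sealed envelopes in randomization blocks of 30". The blocks belong to sites: "Each of 4 sites will be allotted an initial block of 30 envelopes, and sets of backup blocks of 30 envelopes". Envelopes carry the patient number, and section VIII (Data Confidentiality) makes that number sequential within site, so position in the block is known.

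Consent is taken before sedation. Of the end of the procedure, the protocol then says: "Eligibility for the study will be assessed at this time". The envelope is opened after official enrolment. One exclusion is explicitly the operator's judgement: "Cardiogenic shock or any clinical instability as assessed by the physician performing the procedure".

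Section IV describes visibly different procedures for the two arms (only one uses a disc), and neither document describes masking. Section IX, Alternatives to Participation, adds: "SSA devices may be used outside of the study depending on local practice and availability".

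The site figure of 30 appears in two forms. Under Study Design, enrolment runs "until each center enrolls a minimum of 30 patients, or a maximum of 180 patients are enrolled". Under Timing of Subject Enrollment, "enrollment may continue until each site enrolls 30 patients". The cap is separate: "The maximum enrollment at any one site shall not exceed 50% of the total study enrollment, or 90 patients".

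The ratio within a block is not given. Study Design plans 60 patients per arm, and the envelope contents are described only as random.

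**The concern.** Sealed envelopes hide the next assignment only if it cannot be worked out from earlier ones. Here the staff know the block length, their position in the block and every past assignment at their site. If blocks are balanced, the remaining envelopes can be counted. The eligibility decision comes immediately before opening, includes a judgement item, and is made by people with that knowledge. A patient expected to draw the band alone could be left out and still receive the disc outside the study.

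Selection of this kind happens before randomization, so the intention-to-treat analysis in the SAP does not correct it. The outcomes most exposed are radial artery occlusion, which is the first-listed primary objective in section III, and access-site complications, which are the primary safety outcome in section VI. Operators have seen how access and the procedure went before they judge eligibility.

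**Working it through.** **1. The plan's own figure.** Section VI gives 120 patients, a 60-minute difference, SD 100, two-sided alpha 0.05 and 90% power. The normal formula gives 59 per arm (118 in total). At 60 per arm, power is 90.8% (normal) or 90.3% (t test). The stated figure reproduces.

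**2. Assumption.** Each block of 2m = 30 holds m = 15 envelopes per arm. The guesser names the arm with more envelopes left.

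**3. Overall predictability.**
- Expected correct guesses = m + 2^(2m−1)/C(2m,m) − 1/2 = 15 + 2.96 = 17.96 of 30, or 59.9%.
- Expected certain assignments = 2m/(m+1) = 30/16 = 1.875 of 30, or 6.25%. Over four sites each completing exactly one block, that is 7.5 of 120.

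**4. By position (exact enumeration).**

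| Patients | Correct guesses |
|---|---|
| 1-10 | 52.9% |
| 11-20 | 57.2% |
| 21-30 | 69.4% |
| 26-30 | 76.6% |
| 30 | 100% |

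The assignment is already certain at patient 29 in 48% of blocks, at 28 in 22% and at 27 in 10%.

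**5. Bias.** Suppose patients enrolled under one guess have risk +h and under the other −h, with no shift when the counts are tied. Patients enrolled under opposite guesses then differ by 2h. Bias in the between-arm difference = h × (correct − incorrect guesses acted on)/15.
- Every guess acted on: (2 × 17.96 − 30)/15 = 0.395h.
- Only the last ten: (2 × 6.944 − 10)/15 = 0.26h.
- Only certain assignments: 1.875/15 = 0.125h.

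As illustration only, h = 5 percentage points gives 2.0, 1.3 and 0.6 points; h = 10 gives 3.9, 2.6 and 1.25 points.

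**6. Time to hemostasis.** With every guess acted on, a shift of 10, 20 or 30 minutes gives a bias of about 4, 8 or 12 minutes. A bias equal to the whole 60-minute planning difference needs a shift of 60/0.395 ≈ 152 minutes. In simulation (four sites of 30, SD 100, 3,000 runs) the type I error was about 5.5%, 8.5% and 16% for shifts of 10, 25 and 50 minutes.

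**7. Alternatives.** Smaller blocks are easier to guess: 70.8% correct for fixed 4, 68.3% for fixed 6, about 67% for random 4/6/8. With one block of 90 per site, the first 30 patients are guessed correctly 51.8% of the time, and no assignment can be certain before patient 46 (45 of one arm must be used first).

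**8. Cost in balance and power.** For the first 30 of a 45:45 block, the SD of the difference in arm counts is 2 × √(30 × 0.25 × 60/89) = 4.5; over four sites it is 4.5 × 2 = 9.0. A 49:71 split is a difference of 22, or 22/9.0 ≈ 2.4 SDs. Its power (t test) is 89.3%, against 90.3% at 60:60.

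**The case against.** The strongest reply is that the key premise is not in the text. If the designations are unrestricted within a block, guessing stays at 50%. That is correct, and every figure from step 3 to step 6 depends on the 15:15 reading. It is nevertheless the natural reading of blocks combined with 60 per arm, and the protocol should state which is meant.

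Second, 30 is a minimum in one place, and sites may use backup blocks up to 90. This stands: a site may stop mid-block, so 7.5 of 120 is conditional. It does not remove the problem, because each completed block ends in the same way.

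Third, there are safeguards. Randomization follows all anticoagulation decisions, most exclusions are objective, section X promises real-time monitoring that covers entry criteria, and section IX allows dismissal for deviations. These limit acting on a guess. They do not make the sequence less predictable, and no record of patients consented but not randomized is described.

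Two stronger readings are tempting. A reader might infer that operators can foresee most later assignments, or that 30 is a badly chosen block size. Neither is supported: guessing is near chance for the first 20 patients, and 30 is harder to guess than small blocks. A reader might also take 0.39h as the expected bias. It is an upper figure that needs every site to act on every guess. Nothing in the documents shows that selection will occur.

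**Conclusion.** The weakness is real but limited. It lies in the combination of one disclosed, fixed block length held by site, a first block boundary that coincides with the site figure of 30, visible assignments, and a partly subjective eligibility check just before opening. On the inferred 15:15 split, about 1.9 of 30 assignments are certain and guessing reaches 69% in the last ten. The possible bias runs from 0.125h to about 0.39h, depending on how much of this is acted on. Because h is assumed and the documents give no rates to support a value, no bias in absolute terms can be claimed.

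For time to hemostasis the effect is likely small against the planned 60 minutes. For occlusion and access-site complications it could matter more, though its size cannot be estimated from the documents. The point warrants an inexpensive improvement before enrolment; it does not show the design to be invalid.

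**What to change.** Before enrolment:
- Remove the block length from the protocol that sites hold, and keep it, with the within-block ratio, in a restricted randomization document.
- Redraw the envelope list so that no balanced boundary falls predictably at patient 30. A longer undisclosed block per site is one option; a block of 90 is an example, not a requirement. A site that reached 90 would meet that boundary too, so the length must stay undisclosed. Do not move to small blocks.
- Have the list held by someone who does not enrol patients. The data center is an option only if that separation is documented, since it is at the principal investigator's institution.
- Record eligibility on the CRF, with signature and time, before the envelope is opened.
- Tabulate patients consented but not randomized, by site and by position in the list.
- Change the plan of 60 per arm to approximately 60 per arm.

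The cost is a new list, a few protocol sentences, one CRF line and one table, with no extra patients or visits. The arms become only approximately equal, with the small loss of power shown in step 8.
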